## 4.6 Duration of Follow Up for PFS and DoR

Patients will be followed for PFS until progression of disease noted or death, whichever occurs first. Patients will be followed for DoR until progression is noted from the best response, start of a new therapy, or death from any cause. Refer to section 1.1 for long-term follow up time points. In the first year, patients will be followed every 3 months. Between years 2 to 5, the patient will be followed every 3-6 months at the discretion of the treating provider. After 5 years, the patient will be followed every 3-12 months at the discretion of the treating provider. Patients removed from study for unacceptable adverse event(s) will be followed until resolution or stabilization of adverse event. Follow up data will be required unless consent is withdrawn. Overall survival follow up for patients who have progressed will be completed according to section 6.9.4.

# 5 STUDY POPULATION

Potential study participants must meet all inclusion criteria and no exclusion criteria to be deemed eligible for trial participation. To ensure subject safety, all subjects must be deemed eligible at the time of study registration and must continue to meet eligibility criteria up to cycle one day one dosing. This eligibility checklist is used to determine subject eligibility and will be filed with the enrolling investigator's signature in the subject research chart.

- 5.1 Inclusion Criteria
- 5.1.1 \_\_\_\_\_ Diagnosis of CLL according to the NCI/IWCLL criteria.

This includes previous documentation of:

a. Biopsy-proven small lymphocytic lymphoma/CLL

# 

- b. Diagnosis of CLL according to the NCI/IWCLL criteria as evidenced by all of the following:
  - 1. Peripheral blood monoclonal B cell population of greater than  $5x10^{9}/L$

- 2. Immunophenotype consistent with CLL defined as:
  - The predominant population of lymphocytes share both B cell antigens [CD19, CD20 (typically dim expression), or CD23] as well as CD5 in the absence of other pan-T-cell markers (CD3, CD2, etc).
  - Clonality as evidenced by κ or λ light chain restriction (typically dim immunoglobulin expression)
- c. Negative FISH analysis for t(11;14)(IgH/CCND1) on peripheral blood or tissue biopsy (e.g. marrow aspirate), or negative immunohistochemical stains for cyclin D1 on involved tissue biopsy (e.g. marrow aspirate or lymph node biopsy).

5.1.2 \_\_\_\_\_ Repeat testing of somatic mutations and FISH analysis must be performed by a CLIA certified laboratory after progression is noted from most recent line of therapy and within 6 months of screening. Primary CLL cells must harbor at least one of these abnormalities:

- Somatic gene mutation testing shows mutation(s) in TP53, ATM, SF3B1, XPO1 and/or POT1
- Cytogenetic FISH analysis shows deletion 17p13 and/or deletion 11q22.3

5.1.3 \_\_\_\_\_ Relapsed or refractory after at least 2 prior lines of therapy, and in the opinion of the treating Investigator are either not eligible for other approved therapies or no approved therapies are expected to have sustained therapeutic benefit.

5.1.4 \_\_\_\_\_ Patient in need of treatment or change in treatment per iwCLL criteria.

 Patients on BTK, PI3K or BCL2 inhibitors may enroll without meeting iwCLL criteria for treatment as long as there is clinical evidence of progression (i.e. increasing lymphocytosis, worsening anemia/thrombocytopenia attributable to CLL disease progression, increasing lymphadenopathy, or worsening patient symptoms) and require change in treatment at the discretion of the treating provider. Patients must still meet all other inclusion/exclusion criteria for enrollment including appropriate washout periods (5.2.2) and relapsed disease after 2 prior lines of therapy with no other approved therapies that are expected to have sustained therapeutic benefit (5.1.3).

- 5.1.5 \_\_\_\_ Age ≥18 years
- 5.1.6 \_\_\_\_ ECOG performance status between 0-2
- 5.1.7 \_\_\_\_\_ Expected life expectancy of at least 12 months per the investigator.
- 5.1.8 \_\_\_\_ The following laboratory or clinical values obtained  $\leq$  42 days prior to enrollment:
  - Absolute neutrophil count ≥1000/µL (G-CSF support is allowed) unless documented bone marrow involvement of CLL
  - Platelets of  $\geq$ 50K/µL unless documented bone marrow involvement of CLL
  - Creatinine Clearance (CrCl) ≥ 45 mL/minute as measured by a 24 hour urine collection or calculated by the Cockcroft-Gault Formula:
    - Males:  $\frac{(140-age) \times weight[kg]}{serum creatinine \left[\frac{mg}{dL}\right] \times 72}$
    - Females:  $\left(\frac{(140-age)\times weight[kg]}{serum\ creatinine\ \left[\frac{mg}{dL}\right]\times 72}\right) \times 0.85$
  - Total bilirubin ≤ 1.5 x institutional ULN unless due to Gilbert's disease. For those patients with previous history of Gilbert's disease, a direct bilirubin should be performed and must be <1.5mg/dL.
  - SGOT (AST)/SGPT (ALT) ≤3.0 x the institutional ULN
  - QTcF ≤470 msec
    - For patients with prolonged AT interval due to bundle branch block, a "corrected value" ≤470 msec and confirmation by cardiologist that patient is asymptomatic and that no other cardiac conduction or cardiac abnormality is present would pose any safety issues for the patient.
    - Recommended correction of QT for patients with bundle branch block are as follows: Patient's QRS is 160 msec, and the measured QT is 510 msec. As the normal QRS is ~120 msec, subtract 120 msec from the measured QRS of the patient (160-120 = 40 msec) and then subtract this result from the measured QT (510-40=470 msec).
  - Pulse oximetry reading of ≥90% on room air

- 5.1.9 \_\_\_\_\_ Able to adhere to study visit schedule and other protocol requirements
- 5.1.10 \_\_\_\_\_ Patients must be able to swallow capsules

5.1.11 \_\_\_\_\_ Patients must be able to receive xanthine oxidase inhibitor and/or rasburicase for tumor lysis syndrome prophylaxis.

5.1.12 \_\_\_\_\_ Patients with a history of hepatitis B (surface antigen or core antibody-positive and PCR positive) must take lamivudine or equivalent drug during study therapy and for one year after completion of all therapy. Patients on IVIG who are core antibody-positive but PCR negative are not mandated to take prophylaxis.

5.1.13 \_\_\_\_\_ Patients who are HIV+ are eligible under the following circumstances:

- Undetectable HIV viral load (laboratory value obtained within the last 6 months prior to enrollment)
- CD4 count ≥200 (laboratory value obtained within the last 6 months prior to enrollment)
- Actively taking antiretroviral therapy (ART)
- Current ART therapy cannot have significant interactions with RP-3500 or Olaparib (Refer to Appendix 5). If current medications do interact, patients should receive alternative ART.

5.1.14 \_\_\_\_ Recovery to baseline or  $\leq$  Grade 1 CTCAE v5.0 from toxicities related to any prior cancer therapy, unless considered clinically not significant by the treating investigator.

5.1.15 \_\_\_\_\_ Female patients capable of reproduction or males who have partners capable of reproduction must agree to the use of an effective contraceptive method during the course of the study and for 6 months following the completion of their last treatment.

5.1.16 \_\_\_\_ Females of childbearing potential must have a negative serum  $\beta$ -Hcg pregnancy test result within 3 days of the first study dose. Female patients who are surgically sterilized or who are >45 years old and have not experienced menses for >2 years may have  $\beta$ -Hcg pregnancy test waived.

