#### ABREVIATIONS

Abbreviation	Definition/Explanation
AE	Adverse event
ALT	Alanine aminotransferase
ASCO	American Society of Clinical Oncology
AST	Aspartate aminotransferase
AV	Atrioventricular
BCVA	Best-corrected distance visual acuity
BICR	Blinded Independent Central Review
β-HCG	Beta-human chorionic gonadotropin
BID	Twice daily
BMI	Body mass index
BP	Blood pressure
BUN	Blood urea nitrogen
CBC	Complete blood count
CFR	Code of Federal Regulations
CHF	Congestive heart failure
CI	Confidence interval
CLIA	Clinical Laboratory Improvement Amendments
CLL	Chronic lymphocytic leukemia
CLcr	Creatinine clearance
Cmax	Maximum observed concentration
Cmin	Trough observed concentration
CMP	Comprehensive metabolic panel
CNS	Central nervous system
CR	Complete response
CRF	Case report form
СТ	Computed tomography
CTCAE	Common Toxicity Criteria for Adverse Events
ctDNA	Circulating tumor DNA
CYP	Cytochrome P450
CQ	Chloroquine

Abbreviation	Definition/Explanation
DILI	Drug-Induced Liver Injury
DoR	Duration of Response
DSMB	Data Safety Monitoring Board
ECOG	Eastern Cooperative Oncology Group
eCRF	Electronic case report form
ECG	Electrocardiogram
Eg	Exempli Gratia (for example)
FDA	Food and Drug Administration
GCP	Good Clinical Practice
GFR	Glomerular filtration rate
GGT	Gamma-glutamyltransferase
GI	Gastrointestinal
GMP	Good Manufacturing Practice
HBsAg	Hepatitis B surface antigen
HBV	Hepatitis B virus
HCV	Hepatitis C virus
HIV	Human immunodeficiency virus
HR	Heart rate
i.e.	Id est (that is)
IEC	Independent ethics committee
IND	Investigational New Drug
INR	International normalized ratio
IRB	Institutional review board
iwCLL	International Working Group on Chronic Lymphocytic Leukemia
LDH	Lactate dehydrogenase
MRI	Magnetic resonance imaging
NIH	National Institute of Health
PD	Pharmacodynamic(s)
PDAC	Pancreatic Ductal Adenocarcinoma
PFS	Progression-Free Survival
РК	Pharmacokinetic(s)

Abbreviation	Definition/Explanation
PO	Per os (administered by mouth)
PR	Partial response
РТ	Prothrombin time
PTT	Partial thromboplastin time
QTc	QT interval corrected
QTcF	QT interval corrected using Fredericia equation
RBC	Red blood cell
RP2D	Recommended Phase 2 Dose
SAE	Serious adverse event
SD	Stable disease
SD-OCT	Spectral-domain ocular coherence tomography
T 1/2	Terminal elimination half-life
TdP	Torsades de Pointes
T max	Time of maximum observed concentration
ULN	The upper limit of normal
VF	Visual field
WBC	White blood cell

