# 7.3 12-Lead Electrocardiograms

Standard 12-lead (with a 10-second rhythm strip) tracing will be used for all ECGs. All subjects will require triplicate 12-lead ECG measurement with tracings approximately one-minute apart which will be performed according to the Schedule of Events. The parameters to be recorded are QT, QTc, PR, and QRS. All ECGs should be conducted pre-dose and Fridericia's formula will be used for all QT correction calculations. The mean QTcF from these ECGs should be recorded.

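### The bundle-branch-block example in 5.1.8 holds a QT with no heart-rate correction to the 470 msec QTcF limit, and does not fit the Fridericia rule in 7.3

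*Combined protocol and SAP*

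**What the plan says.** Section 5.1.8 (Inclusion Criteria) requires "QTcF ≤470 msec". The abbreviation list defines QTcF as "QT interval corrected using Fredericia equation", so the limit is on a rate-corrected scale.

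For an interval prolonged by bundle branch block, the same criterion accepts "a 'corrected value' ≤470 msec and confirmation by cardiologist that patient is asymptomatic", and the cardiologist must also confirm that no other cardiac abnormality raises a safety issue. The recommended correction is given as an example:

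- Data: "Patient's QRS is 160 msec, and the measured QT is 510 msec".
- QRS excess over a normal of about 120 msec: "subtract 120 msec from the measured QRS of the patient (160-120 = 40 msec").
- Last step: "then subtract this result from the measured QT (510-40=470 msec").

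No heart rate or RR interval appears. Section 7.3 (12-Lead Electrocardiograms) states that "Fridericia's formula will be used for all QT correction calculations". Section 5.1.8 does not say whether the QRS-adjusted QT must then be rate-corrected.

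**The concern.** The exception corrects for QRS width only, then uses a threshold that its parent criterion sets for an interval corrected for heart rate. A site that follows the example step by step compares values on two different scales. A site that starts from 7.3 adds a Fridericia step and may classify the same ECG differently.

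This is a safety eligibility rule. Section 5 ties eligibility to subject safety and makes these criteria a checklist signed by the enrolling investigator. After screening, the Schedule of Events lists ECGs only on days 1 and 3 of cycle 1, so the entry criterion carries much of the planned QT protection.

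**Working it through.** **Inputs.** From 5.1.8: measured QT 510 msec, QRS 160 msec, normal QRS 120 msec, limit 470 msec. From 7.3: Fridericia's formula, QTcF = QT / RR^(1/3), with RR = 60/HR in seconds. Heart rate is not given, so 45 to 100 bpm is assumed.

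**The plan's own figure.** Adjusted QT = 510 − (160 − 120) = 510 − 40 = 470 msec. This reproduces exactly and contains no rate term.

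**Fridericia applied to the example.** Column A adjusts for QRS first: 470 / RR^(1/3). Column B applies Fridericia first: 510 / RR^(1/3) − 40. The last column is the largest adjusted QT whose QTcF is still 470: 470 × RR^(1/3). All values are in msec.

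| HR (bpm) | A | A minus 470 | B | Adjusted QT at QTcF 470 |
|---|---|---|---|---|
| 45 | 427.0 | −43.0 | 423.4 | 517.3 |
| 50 | 442.3 | −27.7 | 439.9 | 499.4 |
| 60 | 470.0 | 0 | 470.0 | 470.0 |
| 70 | 494.8 | +24.8 | 496.9 | 446.5 |
| 80 | 517.3 | +47.3 | 521.3 | 427.0 |
| 90 | 538.0 | +68.0 | 543.8 | 410.6 |
| 100 | 557.2 | +87.2 | 564.7 | 396.4 |

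For example, at 80 bpm RR = 0.75 s, RR^(1/3) = 0.9086, and 470 / 0.9086 = 517.3.

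The order of the two corrections matters little here. A and B differ by 3.6 msec at 45 bpm, 5.8 at 90 and about 7.5 at 100. Both orders give the same direction at every rate.

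**Above 60 bpm.** At 80 bpm, any adjusted QT above 427 and up to 470 msec meets the numeric rule although its QTcF exceeds 470. An adjusted QT of 440 gives 484.3 at 80 bpm (over the limit) but 463.2 at 70 bpm (within it). The size of the excess therefore depends on both the patient's QT and the heart rate.

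**Below 60 bpm.** The exception is an extra route. A patient whose ordinary QTcF is at or below 470 already qualifies under the parent criterion. Two illustrative patients at 50 bpm (RR^(1/3) = 1.2^(1/3) = 1.0627) show the difference:

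- QT 490, QRS 130: adjusted QT is 480, which fails the exception. Unadjusted QTcF is 490 / 1.0627 = 461, so the patient is eligible anyway.
- QT 520, QRS 160: adjusted QT is 480, which fails the exception. Unadjusted QTcF is 520 / 1.0627 = 489, which fails the parent criterion. QRS-adjusted QTcF is 480 / 1.0627 = 452, which is within 470. This patient is refused.

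At 50 bpm, wrongful refusal therefore needs a measured QT above about 499 msec together with an adjusted QT above 470 and up to 499.

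**The case against.** The strongest reply is that 7.3 already supplies the missing step. The parent criterion is a QTcF, QTcF means Fridericia-corrected, 7.3 covers all QT corrections, and the example may illustrate only the QRS subtraction. This reading cannot be excluded, but it fits poorly with an example that calls its output the correction and ends exactly on the limit. Even if it is right, the example is incomplete and would mislead.

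Several limiting points stand:

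- **The number alone admits nobody.** A reader might infer that the example patient is eligible at any heart rate. The documents do not support that, because cardiologist confirmation is also required. That confirmation covers symptoms and other abnormalities, however, and does not ask for a rate-corrected QT.
- **The excess is conditional.** A reader might infer that the exception generally admits patients far above the limit. The discrepancy is zero at 60 bpm, and the larger figures need the faster assumed rates.
- **No baseline problem follows.** A reader might infer that on-treatment QTcF would be compared with an entry value on another scale. Section 7.3 has Fridericia-corrected mean QTcF recorded for all scheduled ECGs, including screening, and no analysis of QTc change from the QRS-adjusted value is planned.
- **Reach is small.** Only patients with QT prolongation from bundle branch block are affected, in a trial expected to enrol about 33 (section 4.4). QT is not an endpoint.

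**Conclusion.** The point holds in a limited form. As written, the example in 5.1.8 sets a QRS-adjusted QT without rate correction against a limit defined as QTcF, and this does not agree with 7.3. For the example's own 470 msec, the gap is about +25 msec at 70 bpm, +47 at 80 and +68 at 90, and −28 at 50. These figures assume the heart rates shown and take the QRS adjustment before Fridericia.

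Above 60 bpm the numeric test can be too lenient. Below 60 bpm it can be too strict, but only for patients who also fail the parent criterion. The number of patients affected cannot be estimated from the documents and is probably small. The correction is still worth making, because a safety entry rule followed literally can misclassify a patient. Nothing here bears on whether 470 msec is the right limit.

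**What to change.** Reconcile 5.1.8 with 7.3. In 5.1.8, state whether the QRS adjustment and the Fridericia correction are both applied before comparison with 470 msec and, if so, in which order. Add a heart rate to the worked example and recompute it under the stated rule. The documents do not settle the choice of rule or order, so it is for the sponsor to make.

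The cost is one sentence and one recomputed example. No new data are needed: 7.3 already records QT, QTc and QRS, and heart rate is a screening vital sign. The downside is that a few bundle-branch-block patients may change eligibility status, in either direction.

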## 5.2 Exclusion Criteria

5.2.1 \_\_\_\_\_ Patients who are currently receiving any other investigational drug. Patients who are or have received therapies for the prevention, treatment or management of COVID-19 under the FDA emergency use authorization are allowed to enroll.

5.2.2 \_\_\_\_ Patients who have received:

- Radiation or chemotherapy ≤2 weeks prior to registration.
- Immunotherapy or targeted therapy ≤2 weeks prior to registration.
  - i. Patients currently on BCR pathway antagonists (i.e. BTK and PI3K inhibitors, etc) require a 2 day wash out period prior to starting combination therapy with RP-3500 and olaparib as these subjects progress quickly after treatment discontinuation.
- Strong CYP3A inhibitors or inducers, p-glycoprotein inhibitors, or BCRP inhibitors within five half-lives or 14 days of registration, whichever is shorter (See Appendix 5).

5.2.3 \_\_\_\_\_ Prior ATR inhibitor use, but prior PARP inhibitor use for any reason is allowed on study.

5.2.4 \_\_\_\_\_ Major surgery 4 weeks prior to C1D1 or who have not fully recovered from major surgery.

5.2.5 \_\_\_\_\_ Evidence of active Richter's Transformation

5.2.6 \_\_\_\_\_ Disease states requiring steroids (e.g. adrenal insufficiency, autoimmune conditions) are allowed as long as the steroid dose is ≤10mg of prednisone or equivalent dose of another steroid. Steroids premedications to prevent iodine contrast allergy for CT scans are allowed.

5.2.7 \_\_\_\_ Patients who have undergone autologous stem cell transplant  $\leq$ 4 weeks or allogeneic stem cell transplant  $\leq$ 12 weeks prior to cycle 1 day 1 or have active graft-versus-host disease are excluded.

5.2.8 \_\_\_\_\_ Patients who have active, clinically significant hepatic impairment (≥ moderate hepatic impairment according to the NCI/Child-Pugh classification)

5.2.9 \_\_\_\_\_ Prior history of another malignancy except for the following:

- Patients with current history of basal or squamous skin carcinoma, cervical carcinoma in situ, localized breast cancer requiring hormonal therapy, or localized prostate cancer (Gleason score <6) are allowed.
- Previously treated malignancies (with chemotherapy, radiation, and/or surgery) currently deemed to have been in complete remission for at least 24 months.

5.2.10 \_\_\_\_\_ Patients with active known central nervous system (CNS) involvement of CLL. Patients with a history of CNS CLL now in remission are eligible for the trial.

5.2.11 \_\_\_\_\_ Patients with uncontrolled concurrent illness including, but not limited to, ongoing or active infection, symptomatic congestive heart failure, extensive bilateral interstitial lung disease, unstable angina pectoris, or psychiatric illness/social situations that would limit compliance with study requirements.

• Patients with a history of pneumonitis or pulmonary disease that could predispose them to development of ILD and/or underlying respiratory conditions should be excluded.

5.2.12 \_\_\_\_ Known prior severe hypersensitivity to RP-3500, olaparib, or any component in its formulations (NCI CTCAE v5.0 Grade  $\geq$  3).

5.2.13 \_\_\_\_\_ Female patients who are pregnant or actively breast feeding

5.2.14 \_\_\_\_\_ Patients with conditions significantly affecting gastrointestinal function including, but not limited to:

- Significant resection of the stomach or small bowel
- Symptomatic inflammatory bowel disease
- Partial or complete bowel obstruction

# 5.3 Registration

Subjects must meet all of the eligibility requirements before registration. Study-related screening procedures can only begin once the subject has signed the consent form. Subjects must not begin protocol treatment prior to registration.

Treatment should start within 14 days after registration.

To register eligible subjects on study, complete a Clinical Trials Office Subject Registration Form and submit to [contact].

For sites outside of Huntsman Cancer Institute, submit registration forms to [contact]

### 5.4 Life Style Considerations

### 5.4.1 Diet

Due to CYP3A4 interactions, subjects will be advised to avoid grapefruit, Seville oranges, pomelos, and star fruit including products containing these fruits (e.g. juices, jams, marmalades, etc.).

### 5.4.2 Contraception

Due to the unknown abortifacient and teratogenic effects of RP-3500 and olaparib, a form of highly effective contraception is required for the duration of study therapy. Female subjects of childbearing potential must use a form of highly effective contraception from the start of study therapy until 6 months after the last dose of study therapy. Male subjects with a partner of childbearing potential must agree to use a method of highly effective contraception from the start of study therapy until 6 months after the last dose of study therapy.

Acceptable highly effective contraceptive methods include:

- Bilateral tubal occlusion
- Vasectomized partner
- Intra-uterine devise (IUD) or hormone-releasing system (IUS)
- Any hormonal (estrogen combined with progesterone or progesterone alone) contraception associated with inhibition of ovulation: implanted, oral, intravaginal, transdermal, or injectable.
- Spermicide with a compatible barrier method (i.e. diaphragm, sponge, or male or female condoms).
- Abstinence from heterosexual intercourse.

It is unknown whether RP-3500 and olaparib can produce drug transfer through seminal fluid. Therefore, male subjects must agree to use a condom during any form of intercourse from the start of study therapy until 6 months after the last dose of study therapy.

#### 5.5 Screen Failures

Screen failures are defined as participants who consent to participate in the clinical trial but do not meet subject eligibility criteria. These subjects will not be entered into the study or begin study intervention. However, minimal information is required to ensure transparent reporting of screen failure participants to meet the Consolidated Standards of Reporting Trials (CONSORT) publishing requirements. Minimal information includes, but may not be limited to, demography, screen failure details, eligibility criteria, and any serious adverse event (SAE) experienced during

screening, but prior to being deemed ineligible. Adverse events and SAEs will not be collected after a subject is deemed ineligible.

Individuals who do not meet the criteria for participation in this trial (screen failure) may be rescreened at the Investigator's discretion.

